6.3. Appendix 3 Demographics and Baseline Characteristics

The number of participants in each analysis set will be summarized overall. In addition, the distribution of participants by country, and site ID will be presented unless otherwise noted.

6.3.1. Demographics

Table 11 presents a list of the demographic variables that will be summarized overall for the FAS.

Table 11: Demographic Variables

Continuous Variables:	Summary Type
Age (years)	Descriptive statistics (N, mean, standard deviation [SD], median and range [minimum and maximum], and IQ range).
Weight at baseline (kg)	
Height at screening (cm)	
Body Mass Index at baseline (BMI) (kg/m ²)	
Number of drinks containing alcohol (weekly period)	
Period of time using substances (beer, wine, distilled spirits) in months derived as = (stop date – start date +1)/30.4375; rounded to 1 decimal point	
Categorical Variables	Frequency distribution with the number and percentage of participants in each category.
Age (≤ 45 years, > 45 years)	
Sex (male, female, undifferentiated)	
Race ^a (American Indian or Alaska Native, Asian, Black or African American, Native Hawaiian or other Pacific Islander, White, Multiple)	
Ethnicity (Hispanic or Latino, not Hispanic or Latino)	
Country (Poland, Taiwan, Japan, New Zealand)	
BMI at baseline (underweight <18.5 kg/m ² , normal ≥18.5-<25 kg/m ² , overweight ≥25-<30 kg/m ² , obese ≥30 kg/m ²)	
History of tobacco use (Yes, No)	
Type of substance use (beer, wine, distilled spirits): current, former, never	

^a If multiple race categories are indicated, the Race is recorded as 'Multiple'

6.3.2. Baseline Characteristics

Table 12 presents a list of the baseline characteristics variables that will be summarized overall for the FAS.

Table 12: Baseline Characteristics Variables

Continuous Variables	Summary Type
HBV history	Descriptive statistics (N, mean, standard deviation [SD], median and range [minimum and maximum], and IQ range).
Duration of infection (years) = (treatment start date – date of HBV infection +1)/365.25; rounded to 1 decimal point	
Time since HBV diagnosis (Years) = (treatment start date – date of HBV diagnosis+1)/365.25; rounded to 1 decimal point	
HBV viral activity and serology parameters	
HBeAg at baseline in IU/mL and log ₁₀ IU/mL (for HBeAg positive participants only)	
HBsAg at baseline in IU/mL and log ₁₀ IU/mL	
HBV DNA at baseline in IU/mL and log ₁₀ IU/mL	

Table 12: Baseline Characteristics Variables

Continuous Variables	Summary Type
HBV RNA at baseline: values in copies/mL and log ₁₀ copies/mL	
HBcrAg at baseline in log ₁₀ U/mL	
HBsAg Antibody (Anti-HBs) at baseline in mIU/mL and log ₁₀ mIU/mL	
Liver Stiffness Measurement at baseline (kPa)	
Categorical Variables	Summary Type
HBV history	Frequency distribution with the number and percentage of participants in each category.
Mode of HBV infection: Sexual transmission, intravenously injectable drug use, blood transfusion, Hemophilia-associated injection, occupational exposure, mother to child transmission, unknown and other	
Type of NA at baseline: TeD, TAF, ETV	
Duration of NA at baseline (years)	
HBV viral activity and serology parameters	
HBeAg status at screening: positive, negative	
HBeAg status at least 6 months before screening (qualitative, based on historical data)	
HBsAg category at baseline (IU/mL): < 1,000, < 10,000, < 100,000, ≥ 10,000	
HBV DNA category at baseline (IU/mL): < LLOQ Target detected (TD) or not detected (TND), < LLOQ TD, < LLOQ TND, < 60, ≥60	
HBV RNA category at baseline (copies/mL): TND, < LOD, < LLOQ, < 1,000, ≥ 1,000	
HBcrAg category at baseline (log U/mL): < 3, ≥ 3 - < 4, ≥ 4	
HBsAg Antibody (Anti-HBs) status at baseline: Positive, Negative	
HBsAg Antibody (Anti-HBs) category at baseline (mIU/mL): < 10, ≥ 10	
HBeAg Antibody (Anti-HBe) status: Positive, Negative	
Baseline ALT toxicity grade according to DAIDS	
Baseline ALT categorization: ≤ 1.0xULN, > 1.0xULN to <2xULN, ≥ 2xULN	

6.4. Appendix 4 Protocol Deviations

In general, the following list of major protocol deviations may have the potential to impact participants' rights, safety or well-being, or the integrity and/or result of the clinical study. Participants with major protocol deviations will be identified prior to database lock and the participants with major protocol deviations will be summarized by category.

- Developed withdrawal criteria but not withdrawn
- Entered but did not satisfy criteria
- Received a disallowed concomitant treatment
- Received wrong treatment or incorrect dose
- Other

All major protocol deviations will be tabulated by coded term for the FAS. A listing of the major protocol deviations will be also presented.

6.5. Appendix 5 Prior and Concomitant Medications

Prior and Concomitant medications will be coded using the World Health Organization Drug Dictionary (WHO-DD). Prior medications are defined as any therapy used before the day of first dose (partial or complete) of study intervention. Concomitant medications are defined as any therapy used on or after the same day as the first dose of study intervention, including those that started before and continue on after the first dose of study intervention.

Summaries of concomitant medications will be presented by ATC class level 2, level 4 and preferred term, analysis phase, and overall. The proportion of participants who receive each concomitant medication will be summarized as well as the proportion of participants who receive at least 1 concomitant medication.

Prior medications will be summarized by overall and ATC class 2, level 4 and preferred term.

6.6. Appendix 6 Medical History

A tabulation of the general medical history coded terms will be provided by body system class and overall.

6.7. Appendix 7 Intervention Compliance

Compliance will be summarized descriptively for the safety analysis set for each study agent (i.e. excluding NA).

Treatment compliance for treatment period 1 and treatment period 2 is defined as follows.

Treatment period 1

- For JNJ-3989: (Total number of injections received/3) * 100%
- For JNJ-6379: (Total medication intake / 4 *a) * 100%

As the 250 mg daily dose of JNJ-6379 consists of 4 tablets (2 tablets of 100 mg strength and 2 tablets of 25 mg strength). The numerator representing the total medication intake for JNJ-6379 is calculated as:

Total medication intake=(Total number of tablets dispensed–Total number of tablets returned).

a: for each participant, the individual period (days) of receiving JNJ-6379 (end date of JNJ-6379 – start date of JNJ-6379)

Treatment period 2

For JNJ-3989 : (Total number of injections received/ 3) * 100%

For PegIFN- α 2a: (Total number of injections received/ 12) * 100%

For JNJ-6379: (Total medication intake/ 4 *a) * 100%

As the 250 mg daily dose of JNJ-6379 consists of 4 tablets (2 tablets of 100 mg strength and 2 tablets of 25 mg strength). The numerator representing the total medication intake for JNJ-6379 is calculated as:

Total medication intake=(Total number of tablets dispensed–Total number of tablets returned).

a: for each participant, the individual period (days) of receiving JNJ-6379 (end date of JNJ-6379 – start date of JNJ-6379)

Compliance to JNJ-6379 will be calculated only for participants who received JNJ-6379.

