5.1.10. Main Groups for Analysis

While most analyses will be focused on all subjects without separating by study intervention, some analysis will be performed in three different groups:

1. Group 1: Participants who received at least one tablet of JNJ-6379 during treatment period 2:
 - Treatment Period 1: JNJ-3989 + JNJ-6379 + NA
 - Treatment Period 2: JNJ-3989 + JNJ-6379 + NA + PegIFN- α 2a
2. Group 2: Participants who did not receive JNJ-6379 at treatment period 2:
 - Treatment Period 1:
 - JNJ-3989 + JNJ-6379 + NA
 - JNJ-3989 + NA
 - Treatment Period 2: JNJ-3989 + NA + PegIFN- α 2a

Some analysis will be performed separately by the study intervention of treatment period 1 and overall.

3. Group 3: all participants who were enrolled in the trial

Post-hoc analyses may be performed based on duration of exposure to JNJ-6379.

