5.6.1. Extent of Exposure

Because of the different route and frequency of treatment administration across the 4 agents (for JNJ-3989 one subcutaneous injection every 4 weeks (Q4W), for JNJ-6379 once daily tablets (QD), for NA once daily tablet (QD), and for PegIFN- α 2a one subcutaneous injection weekly (QW)) the total duration of exposure (weeks) will be calculated for each agent as follows:

- JNJ-3989: $[\text{Min} ((\text{Date of last JNJ-3989 injection in the given phase} + 27 \text{ days}), \text{Date of trial disposition, cut-off date}) - \text{Date of first JNJ-3989 injection in the given phase} + 1] / 7$
- NA: $[\text{Min} (\text{Date of the last NA administration in the given phase, Date of discontinuation from NA, Date of trial disposition, Date of clinical cut-off}) - \text{Date of first NA administration date in the given phase} + 1] / 7$
- PegIFN- α 2a: $[\text{Min} (\text{Date of the last PegIFN-}\alpha\text{2a injection} + 6 \text{ days, Date of discontinuation from PegIFN-}\alpha\text{2a, Date of trial disposition, cut-off date}) - \text{Date of first PegIFN-}\alpha\text{2a injection} + 1] / 7$

The total duration of exposure (weeks) to JNJ-6379 will be calculated for participants who received JNJ-6379 as follows:

- JNJ-6379: $[\text{Min} (\text{Date of the last JNJ-6379 administration in the given phase, Date of treatment disposition for JNJ-6379, Date of trial disposition, Date of clinical cut-off}) - \text{Date of first JNJ-6379 administration in the given phase} + 1] / 7$

Cutoff dates will be defined to match the prespecified timepoints for DRC periodical data reviews, interim analyses and the primary analysis, respectively (see Section 5.8).

Descriptive statistics for duration of each study treatment within a study intervention (N, mean, SD, median, and range (minimum, maximum)) during the 24 weeks of treatment (treatment period 1 and 2) will be summarized. The duration of treatment with NA will be summarized also for the FU phase. Those participants who stopped NA treatment at or before Week 24 and never restarted NA treatment thereafter will be counted as having zero weeks of NA exposure during the FU phase.

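### The JNJ-6379 compliance formula in SAP Appendix 7 omits the +1 day that SAP 5.6.1 uses for exposure, so on its natural reading full adherence scores above 100%

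*SAP*

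**What the plan says.** SAP 6.7 (Appendix 7) gives the same JNJ-6379 expression under both treatment periods. The period 1 line reads "For JNJ-6379: (Total medication intake / 4 *a) * 100" percent. The factor 4 is the number of tablets per day: "As the 250 mg daily dose of JNJ-6379 consists of 4 tablets (2 tablets of 100 mg strength and 2 tablets of 25 mg strength". Its numerator is defined by "Total medication intake=(Total number of tablets dispensed–Total number of tablets returned". The quantity a is "the individual period (days) of receiving JNJ-6379 (end date of JNJ-6379" minus the corresponding start date. No day is added, no phase is named, and the end date is not defined.

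SAP 5.6.1 handles exposure to the same drug differently. It takes the earliest of several end dates, one of which is the last administration in the phase, subtracts "Date of first JNJ-6379 administration in the given phase", adds 1, and divides by 7 to give weeks.

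Two other places bear on how short exposure could be. SAP 1 and 1.2 say that participants had to stop JNJ-6379 immediately. SAP 5.1.10 defines "Group 1: Participants who received at least one tablet of JNJ-6379 during treatment period 2".

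**The concern.** A participant dosed daily from a start date to an end date, both included, has end minus start plus 1 dosing days. The denominator in Appendix 7 is one day short of that, while the numerator counts the tablets of every day. Someone who takes everything therefore scores above 100%, and someone who misses one whole day in the middle scores exactly 100%. The relative error grows as exposure shortens, and at a single dosing day the denominator is zero.

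The SAP counts inclusively elsewhere: in 5.6.1, in the study-day definition (5.1.2.1), in time to event from first intake (5.4.1.3.1) and in duration of infection (6.3.2). Appendix 7 gives no reason to depart from that. Exposure and compliance for one participant on one drug would rest on different day counts. At stake is whether the compliance table for JNJ-6379 reports correct figures.

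**Working it through.** The documents state no compliance percentage, so there is none to reproduce. The one figure that can be checked is the tablet count: 2 × 100 mg + 2 × 25 mg = 250 mg from 4 tablets, which is right.

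**Inputs**
- Tablets per day: 4 (SAP Appendix 7).
- Numerator: tablets dispensed minus returned (SAP Appendix 7).
- a = end date − start date (SAP Appendix 7).
- Inclusive day count for JNJ-6379 exposure: last − first + 1 (SAP 5.6.1).

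**Assumptions for the main calculation**, none of them stated in Appendix 7: the end date is the date of last intake; a is counted within the treatment period; the denominator is 4 × a.

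**Full adherence over D dosing days.** Tablets taken = 4D and a = D − 1, so

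compliance = 100 × 4D / [4(D − 1)] = 100 × D/(D − 1) %.

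| D (days) | As written | With +1 |
|---|---|---|
| 84 (full 12 weeks) | 100 × 84/83 = 101.2% | 100% |
| 28 | 100 × 28/27 = 103.7% | 100% |
| 14 | 100 × 14/13 = 107.7% | 100% |
| 7 | 100 × 7/6 = 116.7% | 100% |
| 2 | 100 × 2/1 = 200% | 100% |
| 1 | 4/0, undefined | 100% |

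The excess is 100/(D − 1) percentage points. It is at most 10 points from D = 11, at most 5 from D = 21 and at most 2 from D = 51.

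**One whole day missed between first and last intake.** Tablets taken = 4(D − 1), so the formula gives 100 × 4(D − 1)/[4(D − 1)] = 100%. The correct value is 100 × (D − 1)/D: 85.7% at 7 days, 92.9% at 14, 96.4% at 28 and 98.8% at 84.

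**Missing brackets.** Read strictly left to right, the expression divides by 4 and then multiplies by a. Seven fully adherent days would give 100 × (28/4) × 6 = 4200%, and one day would give 100 × (4/4) × 0 = 0%.

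**Dates not restricted to the phase.** Take 84 days in period 1 followed by 28 in period 2, all tablets taken. If a uses whole-exposure dates, a = 84 + 28 − 1 = 111. Period 1 compliance is then 84/111 = 75.7% and period 2 compliance is 28/111 = 25.2%. On this reading compliance is understated.

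**The case against.** Five points can be made on the other side.

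1. The inflation figures rest on a particular reading. If the end date were recorded as the first day off drug, end minus start would be the correct count. If a covered the whole exposure, a Group 1 participant with a full 84-day period 1 and one day in period 2 would have a = 84. Nothing would be divided by zero, and period 2 compliance would come out at 4/(4 × 84) = 1.2%, too low instead of too high. This stands as a limit on the figures. It does not rescue the formula, because the text leaves both terms open. SAP 5.6.1, with its last administration date and its restriction to a phase, makes the reading used here the likelier one.

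2. The bracket defect and the division by zero cannot both apply: read left to right, one day gives 0%. That is correct. Because Appendix 7 explains what the 4 stands for, a programmer would probably infer 4 × a, so the bracket point is one of notation.

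3. A reader might infer that very short period 2 exposures are to be expected, and so that compliance is badly inflated in Group 1. The documents do not support that. They give no distribution of JNJ-6379 exposure, and a rule requiring at least one tablet assigns participants to a group without showing that any had so little. Such exposures are possible; their number is unknown.

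4. A reader might also infer that efficacy or safety results are affected. They are not. Appendix 7 only summarises compliance descriptively; there is no per-protocol set or compliance threshold, and Groups 1 to 3 are not defined by it.

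5. Other adherence information remains. SAP 5.6.1 calculates exposure with the extra day, and separately counts participants who skipped any dose and those who missed more than five JNJ-6379 doses within a four-week period. This stands, and it limits the harm.

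**Conclusion.** Wrong as written, but minor. The conflict between Appendix 7 and 5.6.1 is plain on the page. On the three assumptions set out in the working, full adherence is overstated by 100/(D − 1) points: 1.2 points for a complete 12-week period, more than 5 points for exposures of 20 days or fewer, and no defined value for a single day. If whole-exposure dates were used instead, the error would run the other way for participants dosed in both periods. How many participants fall in the range where this matters cannot be told from the documents. The consequence is confined to a descriptive table for a withdrawn agent.

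**What to change.** In SAP Appendix 7, under both treatment periods:

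- define a = date of last JNJ-6379 intake in the period − date of first JNJ-6379 intake in the period + 1;
- write compliance = [total tablets taken in the period / (4 × a)] × 100%.

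This gives 100% for full adherence at every duration, including one day. It removes the ambiguity over brackets, end date and phase, and brings the day count into line with 5.6.1. The cost is two lines of SAP wording and the matching change in the program. No new data are needed, and no other analysis changes.

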4. STUDY DESIGN

4.1. Overall Design

This ISA describes a Phase 2a study of the combination regimen of JNJ-3989 with NA and PegIFN- α 2a. Prior to Protocol Amendment 3, the study intervention also included JNJ-6379. This ISA is a companion document to the Master Protocol PLATFORMPAHPB2001, which describes the common design elements of the Platform study in participants with CHB. This ISA describes specific and/or additional protocol elements applicable to this open-label, single-arm, multicenter, interventional study to evaluate the efficacy, safety, tolerability, and PK of the combination of JNJ-3989, NAs, and PegIFN- α 2a in approximately 50 patients with CHB.

Note that as of Protocol Amendment 3, JNJ-6379 has been removed as study intervention and the study will continue with JNJ-3989, NA and PegIFN- α 2a only. Participants had to stop JNJ-6379 treatment immediately.

Approximately 50 virologically suppressed CHB-infected participants, 18-65 years (inclusive) of age, will be enrolled in this study. Approximately 40% HBeAg-positive participants will be enrolled.

This open-label study will be conducted in 4 periods:

- Screening Period (4 weeks [if necessary, can be extended to a maximum of 8 weeks decided on a case-by-case basis and in agreement with the sponsor]).
- Treatment Period 1 (12 weeks) consisting of combination treatment with JNJ-3989 + NA.
- Treatment Period 2 (12 weeks) adding PegIFN- α 2a to the combination treatment regimen of Treatment Period 1.
- Follow-up (FU) Period (48 weeks).

The total duration of individual participation will be up to 76 weeks (including 4 weeks of screening).

Enrolled participants will start Treatment Period 1 with the following combination treatment regimen for a duration of 12 weeks:

200 mg JNJ-3989 (subcutaneous injection Q4W) +

NA (tablets QD): tenofovir disoproxil (245 mg), or TAF (25 mg), or ETV (0.5 mg). At Week 12, participants who still meet the eligibility criteria for PegIFN- α 2a (see Section 5.2, Exclusion Criteria) will start Treatment Period 2 for a duration of 12 weeks:

200 mg JNJ-3989 (subcutaneous injection Q4W) +

NA (tablets QD): tenofovir disoproxil (245 mg), or TAF (25 mg), or ETV (0.5 mg) +

180 µg PegIFN-α2a (subcutaneous injection once weekly). Participants no longer meeting the PegIFN-α2a eligibility criteria at Week 12 will continue with the Period 1 treatment until Week 24.

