4. POPULATIONS (ANALYSIS SETS) FOR ANALYSIS

Due to a potential impact of future Coronavirus Disease (COVID-19) pandemics on the study data collection, study treatment adherence and study conduct, the modified Full Analysis Set (mFAS) and modified IFN-FAS (mIFN-FAS) are defined to target the estimation of effects without the pandemic-related influences.

The primary set for the efficacy analyses will be the FAS set, and for the safety analyses the safety set. The IFN-FAS and modified FAS/IFN-FAS analysis sets will be used if there is a difference of at least 2 participants between analysis sets.

Table 2: Analysis Sets for Analysis

Analysis Sets	Description
Screened	All participants who signed the ICF for the Master Protocol and an ICF specific for the ISA.
Enrolled	All participants who were enrolled in this ISA.
Full Analysis Set (FAS)	All participants who were enrolled and who received at least 1 dose of study intervention within this ISA.
Modified FAS	All participants who were enrolled and who received at least 1 dose of study intervention excluding those participants who, because of COVID-19 or similar pandemics related reasons, withdrew prematurely from the study prior to Week 24 (end of study intervention [EOSI]), or had no efficacy assessment for the primary endpoint. COVID-19 or similar pandemics related reasons may include for example missed visits due to travel restriction, shortage of lab kits at the planned visit, missed collection of blood sample at key time points for the primary efficacy endpoint, etc.
IFN-FAS	All participants who were enrolled and who received at least 1 dose of PegIFN- α 2a within this ISA.
Modified IFN-FAS	All participants who were enrolled and who received at least 1 dose of PegIFN- α 2a excluding those participants who, because of COVID-19 or similar pandemics related reasons, withdrew prematurely from the study prior to Week 24 (EOSI), or had no efficacy assessment for the primary endpoint. COVID-19 or similar pandemics related reasons may include for example missed visits due to travel restriction, shortage of lab kits at the planned visit, missed collection of blood sample at key time points for the primary efficacy endpoint, etc.
Safety	All participants who received at least 1 dose of study intervention. Participants will be analyzed according to the study intervention they actually received.

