5.8.3.1. Data Reviews

The DRC will periodically review unblinded cumulative safety and efficacy data at the following timepoints:

- DR1: 20 participants have reached the Week 12 (end of treatment period 1) time point or discontinued earlier.
- DR2: 20 participants have reached the Week 16 time point or discontinued earlier.
- DR3: 20 participants have reached the FU Week 12 time point or discontinued earlier.
- DR4: 20 participants have reached the FU Week 48 time point or discontinued earlier.

Safety data comprising AEs, SAEs, AEs of special interest, laboratory data, electrocardiogram (ECG) data and any other data applicable for the study, will be summarized, plotted and provided as appropriate.

Besides the safety variables listed above, selected efficacy parameters for review may include values and changes from baseline over time in HBV disease blood markers (such as HBsAg, HBeAg, HBV DNA and ALT), proportion of participants with virologic breakthrough, and flares.

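### PegIFN and JNJ-3989 compliance is divided by a fixed full course, so participants who missed no due injection can score 0% or 33%

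*SAP*

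**What the plan says.** SAP Appendix 7 (section 6.7) sets the population: "Compliance will be summarized descriptively for the safety analysis set for each study agent (i.e. excluding NA"). The safety set in SAP section 4 does not require PegIFN: "All participants who received at least 1 dose of study intervention. Participants will be analyzed according to the study intervention they actually received".

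The formulas are:

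- JNJ-3989, Period 1: "For JNJ-3989: (Total number of injections received/3) * 100" percent. Period 2 uses the same divisor of 3.
- PegIFN, Period 2: "Total number of injections received/ 12) * 100" percent.
- JNJ-6379: tablets taken over four per day times an individual number of days, "a: for each participant, the individual period (days) of receiving JNJ-6379". A closing rule adds: "Compliance to JNJ-6379 will be calculated only for participants who received JNJ-6379". No such rule is given for PegIFN or JNJ-3989.

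The protocol provides for participants who do not receive the full course. Section 4.1 says that those who no longer meet the PegIFN "eligibility criteria at Week 12 will continue with the Period 1 treatment until Week 24". Section 7.1 lists criteria under which JNJ-3989 and PegIFN must be stopped, and further criteria for PegIFN alone.

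SAP 5.6.1 refers to Appendix 7 for compliance. The exposure-duration formulas in 5.6.1 include the cut-off date, and the PegIFN formula also includes the date of discontinuation. The compliance formulas include neither.

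**The concern.** A compliance percentage should tell the reader whether participants took what they were due to take. With a full-course divisor for everyone, the figure also falls when the protocol itself withholds or stops an agent. One table would then mix missed injections with injections that were never due, and would set these figures beside JNJ-6379 figures built on a different principle. In a single-arm study, a reader could take a low PegIFN percentage as a sign of poor adherence that did not occur, and use it to explain a weak HBsAg result.

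The second issue is the period boundary. SAP Table 3 starts Period 2 at the first PegIFN injection for those who receive it, whereas the divisor of 3 assumes that the Week 12 JNJ-3989 injection belongs to Period 2.

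**Working it through.** **The plan's divisors.** The Schedule of Activities gives JNJ-3989 on Day 1 and at Weeks 4 and 8 (3 injections), then at Weeks 12, 16 and 20 (3 injections). PegIFN is weekly from Week 12 to Week 23 (12 injections). The figures 3, 3 and 12 are therefore right for a full course. The question is whether they suit participants for whom a full course was not due.

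**No due dose missed, scored by the SAP formula (received / fixed divisor):**

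- Ineligible for PegIFN at Week 12: 0/12 = 0%.
- PegIFN stopped under Protocol 7.1 after 1, 4, 6, 8 or 11 injections: 8.3%, 33.3%, 50.0%, 66.7%, 91.7%.
- JNJ-3989 stopped after 1 or 2 injections in a period: 33.3%, 66.7%.

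With injections due up to the stop as divisor, each stopped participant scores 100%. The ineligible participant becomes not applicable.

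**Effect on a mean.** The documents give no counts of ineligible or stopped participants, so these are assumed illustrations for N = 50 with no missed dose:

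- 5 ineligible, 45 full course: (45 × 100 + 5 × 0)/50 = 90%.
- 5 stopped after 6 injections, none ineligible: (45 × 100 + 5 × 50)/50 = 95%.
- 2 ineligible, 3 stopped after 6: (45 × 100 + 3 × 50)/50 = 93%; among the 48 recipients, 4650/48 = 96.9%.
- 5 ineligible, 5 stopped after 6: (40 × 100 + 5 × 50)/50 = 85%; among the 45 recipients, 4250/45 = 94.4%.

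The individual divisor gives 100% in all four.

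**Cuts during treatment.** The second data review (SAP 5.8.3.1) is set for when "20 participants have reached the Week 16 time point or discontinued earlier". A participant just reaching Week 16 has had 4 or 5 PegIFN injections, depending on whether that week's dose is counted: 33.3% to 41.7%. For JNJ-3989 in Period 2 it is 1 or 2 of 3: 33.3% to 66.7%. SAP Table 10 lists extent of exposure at this review. That compliance is included is an inference from its place in 5.6.1.

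**Period boundary.** Suppose PegIFN starts at least one day after the Week 12 JNJ-3989 injection, and injections are assigned to periods by Table 3. Period 1 then holds the injections of Days 1, 29, 57 and 85, and Period 2 those of Days 113 and 141.

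- Compliance: 4/3 = 133% and 2/3 = 67%.
- JNJ-3989 exposure by the 5.6.1 formula, (last injection + 27 − first injection + 1)/7: Period 1 is (85 + 27 − 1 + 1)/7 = 16 weeks; Period 2 is (141 + 27 − 113 + 1)/7 = 8 weeks.
- On schedule: (57 + 27 − 1 + 1)/7 = 12 and (141 + 27 − 85 + 1)/7 = 12 weeks.

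The combined total is 24 weeks either way.

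**The case against.** Received over planned course is a legitimate descriptive measure, and the SAP gives the reader other means to separate stopping from missing. Section 5.2 tabulates discontinuation of study interventions with reasons. Section 5.6.1 reports duration by agent, participants who skipped any dose, and those who missed two or more JNJ-3989 or PegIFN injections. The individual JNJ-6379 divisor also has a stated reason: SAP Amendment 1 changed it because the agent was withdrawn during the study. This stands as a reason to rate the matter low. It does not justify putting two definitions under one label.

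The safety-set clause about intervention actually received could be read as leaving ineligible participants out of the PegIFN summary. That reading is possible. But the appendix spells out a recipients-only rule for JNJ-6379 alone, so the text should say which is meant.

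Some stronger inferences are not supported:

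- That participants are classed as non-compliant. The SAP sets no threshold, and compliance defines no analysis set.
- That every early stopper is affected in both periods. Under Table 3, someone who stops before Week 12 has no Period 2, so no 0/12 arises there.
- That 5/12 is the most an adherent participant can reach at the Week 16 review. The data are cumulative, and participants enrolled earlier may be well past Week 16.
- That a one-day PegIFN delay is expected. The Schedule of Activities places both injections at Week 12. Self-injection, the eligibility recheck and the permitted two-day vaccination delay make a later start possible, but its frequency is unknown.

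**Conclusion.** The point holds as a reporting defect of low priority. Taken literally, Appendix 7 gives 0% for a participant ineligible for PegIFN at Week 12 and 33% for one stopped under Protocol 7.1 after four PegIFN injections, with no due dose missed in either case. It also puts these agents on a different scale from JNJ-6379. The 0% depends on ineligible participants being counted in the PegIFN summary, which the text implies but does not state.

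The primary endpoint is unaffected. Outputs cut while participants are on treatment would also be lowered, if they include compliance. The primary and final analyses would not be lowered by a cut-off, because by then all participants have completed Week 24 or discontinued. The 133%/67% and 16/8-week figures are conditional on a later PegIFN start and a split by Table 3. Group means from 85% to 95% are assumed illustrations, not predictions.

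**What to change.** In SAP Appendix 7:

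1. Calculate PegIFN compliance only in participants who received PegIFN.
2. For PegIFN and JNJ-3989, use as denominator the injections due up to the earliest of discontinuation of that agent, study withdrawal or data cut-off.
3. Assign JNJ-3989 injections to periods by scheduled visit: Day 1, Weeks 4 and 8 to Period 1; Weeks 12, 16 and 20 to Period 2. Use the same assignment wherever JNJ-3989 exposure is shown by period.
4. If the percentage of the planned full course is also wanted, report it separately under that label.

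No change is needed to the reporting of early stopping in SAP 5.2 and 5.6.1. The cost is a few lines of SAP text and one derived denominator. Injection, discontinuation and cut-off dates are already needed for the exposure analysis, so no new data are required.
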